## **4. Study Design and Methods**

### **a. Study overview**

Healthy male and female volunteers will be recruited and informed that they may be eligible to participate in a study that examines the role of different sensory fibers in perceiving how touch feels. We will explain that participants will participate in a single session of about 2 hours in length. We will place an ischemic-compression

block with a tourniquet that will cut off blood flow to one arm, and then rate their perception of sensory stimuli on both arms. The purpose of the study is to identify the role of A-beta, A-delta, and C-fibers in the perception of deep pressure touch. See [Figure 1](#) for study flow. All visits will be on an outpatient basis and all experiments will be conducted in Building 10 of the NIH.

Subjects will also be informed that they may withdraw from participation at any time during the course of the study and that they will be compensated for each portion of the study that they have completed.

### **b. Recruitment**

We anticipate recruiting up to 24 potential participants. Participants will be recruited from our currently active NCCIH Phenotyping protocol (16-AT-0077). When a potential subject contacts us, he or she will be scheduled for a telephone pre-screening session (described below). Cold-calling will not be used to contact or recruit potential participants. NCCIH employees cannot participate in this protocol. The anticipated accrual rate is approximately four participants per month. With the accrual ceiling set at 24 participants and expected rate of enrollment of 4 participants per month, it may take approximately 6 months to reach accrual target and another 12 months to complete data analysis for a total study duration of 18 months.

#### **Telephone Interview (pre-screening)**

A pre-screening telephone call of approximately 10 minutes will be conducted to determine eligibility (see Attachment 1 for details). During the telephone interview, the subject will be informed about the general procedures of the study, and inclusion/exclusion criteria will be assessed. If the potential subject does not meet these criteria, the interview will be terminated and pre-screening information will be destroyed. However, if the potential participant agrees, we will retain their contact information to contact them later about other studies in the lab for which they may be eligible (including name, email, and phone number). Potentially eligible subjects will be told that to serve as participants they will be

required to undergo a drug screening and, for participants who can become pregnant, a pregnancy test. If the potential subject agrees to continue to participate, they will be scheduled for the single study session. Further screening information will be drawn from previous participation in the NCCIH Phenotyping Protocol, 16-AT-0077. Participants will be informed of this.

### **c. Screening**

Screening will be accomplished under NCCIH protocol 16-AT-0077, and the following procedures will be performed to assess eligibility:

- Urine collection for pregnancy screening (within 24 hours of testing for participants who are able to become pregnant) and drug screening (“Drug Abuse Screen Qualitative, urine”; panel includes Amphetamines, Benzodiazepine, Opiates, Cocaine metabolites, and Cannabinoids).
- Physical exam and medical history (within one year of screening unless otherwise specified) to assess the following:
  - Congenital upper limb deficiency or amputation
  - Peripheral neuropathy
  - Dermatological conditions that would influence cutaneous sensitivity
  - Assessment of current medications and treatments including use of pain medications; topical pain relieving creams; and medications that increase risk of seizures
  - Major medical conditions including psychiatric conditions and alcohol or substance use disorders
  - History of clotting and circulatory disorders
  - History of seizures and seizure disorders
  - History of fainting with blood draws
  - Ability to fit in inflated arm blood pressure cuff

If deemed eligible, the participant will provide consent for the current protocol prior to performing any procedures specific to this protocol.

The consent form will be explained and all questions will be answered before the participant is asked to sign the consent form (see Section 14 for details). Consent may occur during an additional, separate visit from the research session.

Consent will be obtained before any study procedures will be done. Once enrolled in the current protocol, a LHP will review eligibility criteria at the beginning of each session, to confirm that participants are eligible and meet day-of-study criteria.

#### d. Study procedures

Participants eligible to proceed will be asked to complete a single session, in the NIH Clinical Research Center.

An LHP will review eligibility criteria at the beginning of each session, to confirm that participants remain eligible and meet day-of-study criteria (5-10 minutes). Then, the nerve block procedure and sensory testing will be performed as depicted in **Figure 1. Study Flow** and described in detail below (approximately 1 hour, all procedures for research purposes):

[figure not shown]

Figure 1. Study Flow

Each nerve block session will follow approximately the timeline shown. Timing is approximate as nerve blocks progress at different speeds for different individuals.

Baseline affective touch testing will be performed on both arms (ratings of the intensity and pleasantness of slow brushing and deep pressure). The tourniquet will be placed by a LHP. Sensory testing will be conducted regularly to monitor block progression and loss of A-beta-associated sensation. When A-beta associated perception has been substantively eliminated, ratings of slow brushing and deep pressure (affective touch) will be repeated on each arm/hand. Sensory monitoring will continue and affective ratings may be repeated if further A-beta or A-delta percepts are lost before C-fiber function (loss of warm perception; this separation is not always observed; [14]). Testing is likely to be completed within 30-40 minutes from block placement. The nerve block will be removed by 60 minutes from placement.

### **Details of Ischemic-compression nerve block**

An ischemic-compression block (see [Figure 2](#) below) will be placed to eliminate A-beta associated sensation. Ischemic-compression blocks affect large myelinated fibers before unmyelinated fibers are affected [14]. The subject will hold one arm over their head for approximately one minute and the LHP will exsanguinate the arm. Half the subjects will be tested on the dominant arm and half on the non-dominant arm to avoid confounds in arm dominance and affective responses. The LHP will then inflate tourniquet to approximately 100mmHg above the subject's systolic blood pressure (BP) (e.g. [13, 14]). The subject will then rest their arm comfortably on a pillow on a table placed in front of them. Sensory testing will be conducted with sight occluded and white noise or similar sounds via headphones to eliminate visual and auditory cues in the sensory tasks.

[figure not shown]

Figure 2. An ischemic-compression block

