## Précis:

**Objective:** The sensory basis of non-painful deep pressure sensation is not known. We recently found that innocuous pressure sensation is eliminated in rare sensory neuronopathy patients with a specific loss of A-beta fibers, strongly suggesting that A-beta fibers underlie the ability to sense deep pressure. In addition, we and others have shown that deep pressure touch (observed in hugs and massage) frequently conveys a sense of pleasantness. The current study aims to examine the role of A-beta fibers in the perception of deep pressure touch including both its intensity and the pleasant affect it often elicits. This study constitutes the second study of the K99 phase of a K99/R00 grant application awarded to [name] by NCCIH.

**Study Population:** Up to 24 healthy participants will be enrolled in the study with a goal of 12 completers. Participants will be invited based on previous screening and participation in our studies.

**Design:** Participants will undergo an ischemic-compression block. Sensory stimuli will be administered at frequent intervals to capture the loss of sensation related to A fibers as the block progresses. Before and after A-beta-associated sensations have been lost, the perception of deep pressure will be tested. Participants will rate the intensity and pleasantness of the pressure. Ratings of pain and discomfort will be collected throughout the study session.

**Outcome measures:** Primary outcome; Rating of intensity of deep pressure on the blocked arm before versus after loss of A-beta sensation, compared to ratings on the unblocked arm.

Secondary outcomes: 1) Rating of pleasantness of deep pressure on the blocked arm after loss of A-beta sensation, compared to ratings on the unblocked arm; 2) Ratings of intensity and pleasantness of gentle brushing on the blocked arm after loss of A-beta sensation, compared to ratings on the unblocked arm.

Precis posted online at [clinicaltrials.gov](https://clinicaltrials.gov): see Attachment 2

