## 3. Subjects

### a. Description of study populations

Based on our power calculations, we would like to have 12 healthy men and women who meet the inclusion/exclusion criteria described below participate in the study. Because of possible dropouts during the study due to discomfort of the nerve block, we will set our maximum accrual at 24 participants (see detailed explanation of sample size estimate on p. 21). Withdrawals/dropouts will be replaced. In accordance with HRPP SOP 14F and provided they are not subordinates, relatives, or co-workers of the investigators, or NCCIH DIR employees, NIH employees may participate in this study.

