## **9. Outcome Measures**

### **Primary outcome measures**

The primary outcome is the change or difference score (pre to post) in intensity ratings of deep pressure measured before and after loss of A-beta-associated sensations on the affected arm versus the unaffected arm (e.g. compared between arms by a paired t-test at the group level).

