### **Secondary outcome measures**

The secondary outcomes include change or differences in pleasantness ratings of deep pressure or intensity or pleasantness ratings of slow brushing and fast brushing before and after loss of A-beta and A-delta-associated sensory function (relative to unaffected arm).

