#### Behavioral Data

All behavioral data will be analyzed using SPSS or similar statistical package. A significance level of  $p < 0.05$  will be adopted for all analyses.

For the primary and secondary outcomes, we will use paired t-test or equivalent nonparametric test to evaluate the effect of the nerve block

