### b. Power analysis

In order to yield meaningful statistical analyses of the psychophysical data, and specifically for our primary outcome measure, we estimate that the sample size required to complete the study would be 12 healthy participants. G\*Power (<http://www.gpower.hhu.de>) was used to compute the necessary sample size. In our recent study of deep pressure perception (manuscript in preparation; data available upon request), the same oscillating deep pressure sequence was rated as an intensity  $M = 4.2$  (scaled to our 0-10 scale); we expect intensity to drop at least 2 points on our 0-10 rating scale (likely more since patients lacking A-beta fibers had no perception of deep pressure in our previous study, Case & [name] et. al., under review). In our previous study healthy participants rated the same deep pressure sequence on two different days and the standard deviation of the change in their rating from Day 1 to Day 2 was 1.7. Based on a

2-point change (due to blocking A-beta fibers which should fully eliminate sensation) and a standard deviation for within-subject rating change scores of 1.7, we expect a Cohen's effect size  $d = 1.17$ . Setting statistical power to 95% and Type I error probability to  $\alpha=0.05$ , 12 subjects would be required to complete the study. We expect up to a 50% dropout rate of participants based on prior NIH studies and the discomfort of prolonged nerve blocks found in other studies [13]. Thus, we will enroll up to 24 participants and dropouts will be replaced.

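### The blocked arm is counterbalanced by dominance, but the planned paired test omits that factor and no rule keeps the half-and-half split among those analysed

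*Combined protocol and SAP*

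**What the plan says.** Section 4d (Details of Ischemic-compression nerve block) states that "Half the subjects will be tested on the dominant arm and half on the non-dominant arm", and gives the purpose: "to avoid confounds in arm dominance and affective responses". It does not say how a participant is assigned to one arm type or the other, or whether the halves refer to people enrolled or people who complete.

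Section 9 defines the primary outcome as the pre-to-post change in deep-pressure intensity "before and after loss of A-beta-associated sensations on the affected arm versus the unaffected arm (e.g. compared between arms by a paired t-test" at group level). Section 10a (Behavioral Data) covers the primary and secondary outcomes together: "we will use paired t-test or equivalent nonparametric test to evaluate the effect of the nerve block". Neither section mentions dominance.

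The secondary outcomes are worded in two ways. The Précis has "Rating of pleasantness of deep pressure on the blocked arm after loss of A-beta sensation, compared to ratings on the unblocked arm", which names no baseline. Section 9 has change or differences "before and after loss of A-beta and A-delta-associated sensory function (relative to unaffected arm").

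On dropout, Section 3a says "Withdrawals/dropouts will be replaced". Section 10b repeats this, expects up to 50% dropout, and caps enrolment at 24 to obtain 12 completers. Neither section says which arm a replacement has blocked.

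**The concern.** A factor that the design balances would normally be carried into the analysis, and the balance would be defined on the people analysed. Here neither is written down. Two different consequences can follow, depending on whether the balance survives.

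- **Balance kept (6:6).** The estimate is fine. Any difference in block effect between the two arm types is left in the error term, so the interval can be wider than it needs to be and power can fall.
- **Balance lost.** The unadjusted mean weights one arm type more heavily. Any such difference then moves the estimate, and the type I error for the dominance-averaged effect can exceed 5%.

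Lost precision is not neutral throughout. Secondary Hypothesis 2 predicts that brushing pleasantness will not decrease, and a noisier comparison makes a non-significant result, the predicted one, easier to obtain.

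**Working it through.** **1. The plan's own figure.** Section 10b gives a 2-point drop, SD 1.7, 95% power and alpha 0.05. The effect size is 2/1.7 = 1.176 (stated as 1.17). For a two-sided paired t-test by the noncentral t, n = 11 gives 93.9% and n = 12 gives 95.9% (95.7% at d = 1.17). Enrolment is 12/(1 - 0.5) = 24. Both stated figures reproduce.

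**2. What cancels and what does not.** Let D = (post - pre, blocked arm) - (post - pre, unblocked arm). If the dominant arm is always rated c points higher, c is in both pre and post and drops out of D. What remains is the gap g: mean D when the dominant arm is blocked minus mean D when the non-dominant arm is blocked. The documents give no value for g, so I assume 0 to 2 points.

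Under the Précis wording of the secondary outcomes, the score is post-block blocked minus post-block unblocked. A constant c then enters as +c or -c according to the arm blocked. The gap is 2c, and no difference in block effect is needed to produce it.

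**3. Split kept at 6:6, residual SD 1.7.**

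- Adjusted (mean of the two stratum means, 10 df): half-width = 2.228 × 1.7/√12 = 1.093.
- Unadjusted (11 df): SD_u = √(1.7² + (g/2)² × 12/11), half-width = 2.201 × SD_u/√12.
- Example, g = 2: SD_u = √(2.89 + 1.091) = 1.995, half-width 1.268.

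Type I error and power are from 400,000 simulated trials per setting.

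| Gap g | SD_u | Unadjusted half-width | Against 1.093 | Unadjusted type I error | Unadjusted power | Adjusted power |
|---|---|---|---|---|---|---|
| 0 | 1.700 | 1.080 | 1.2% narrower | 5.0% | 96.0% | 95.6% |
| 0.5 | 1.720 | 1.093 | equal | 4.7% | 95.7% | 95.6% |
| 1 | 1.778 | 1.130 | 3.3% wider | 4.2% | 94.9% | 95.6% |
| 2 | 1.995 | 1.268 | 16% wider | 2.4% | 91.5% | 95.6% |

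Break-even: g = 2√[((2.228/2.201)² - 1) × 1.7² × 11/12] ≈ 0.51 points.

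**4. Split not kept.** Suppose 24 are enrolled 12:12 and 12 complete independently of dominance (hypergeometric).

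- P(6:6) = 924²/2,704,156 = 32%
- P(7:5) = 2 × 792²/2,704,156 = 46%
- P(8:4 or worse) = 22%
- P(9:3 or worse) = 3.9%

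The unadjusted mean shifts by g × (8/12 - 1/2) = 0.17g at 8:4 and by g × (9/12 - 1/2) = 0.25g at 9:3.

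| Split | Unadjusted type I error, g = 1 | Unadjusted type I error, g = 2 | Adjusted type I error | Adjusted power |
|---|---|---|---|---|
| 8:4 | 5.2% | 5.6% | 5% | 93% |
| 9:3 | 6.6% | 10.4% | 5% | 89% |

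Adjustment therefore restores the error rate but not the power lost to imbalance. Only keeping the split does that.

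**The case against.** A reader might infer that the planned intervals are too wide and that replacement breaks the balance. The documents support neither as a statement of fact.

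- **Width.** The ordinary confound, one arm simply being rated higher, is removed by the change scores that Section 9 uses. Only a gap in the between-arm change difference can widen the primary interval, and no passage reports or predicts one. With no gap the planned interval is correct and slightly the narrower of the two. The split in Section 4d is a precaution, not a claim that the block works differently by dominance.
- **Size of the assumed gap.** A 2-point gap means a drop of 3 points in one arm type and 1 in the other. The 2.4% type I error also needs an odd null, with opposite effects of 1 point in the two arm types. If the block does nothing in either, the gap is zero and this loss does not arise.
- **Balance.** The documents are silent rather than wrong. The halves could mean completers, and staff could keep the vacated arm type in practice. The 22% is for the full 50% dropout. On the same reasoning, P(8:4 or worse) is 2 × 70/1,820 = 7.7% if 16 are enrolled (8:8), and 2 × (9 × 126 + 84)/18,564 = 13.1% if 18 are enrolled (9:9). If completion is unrelated to dominance, the shift averages to zero over repetitions.

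All of this stands, and it limits the size of the point. It does not supply the missing rule for replacements or the missing analysis statement. It also does not cover the Précis wording of the secondary outcomes, where a plain arm difference does not cancel.

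**Conclusion.** The point holds as a conditional one and is minor for the primary outcome. The design balances on dominance, the analysis does not name it, and nothing written keeps the balance among the 12 analysed. Over an assumed gap of 0 to 2 points at a kept 6:6 split, the cost of leaving the factor out ranges from a slight gain to a 16% wider interval and about 4 points of power. If the split is lost, the estimate moves by 0.17 points (8:4) or 0.25 points (9:3) per 1-point gap, against an expected effect of 2. These are alternatives: excess width belongs to a kept balance, a shifted estimate to a lost one.

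The exposure is larger for the secondary outcomes if the Précis wording governs, because a plain dominance difference of 0.5 points would then act as a 1-point gap. Pleasantness is also the kind of affective response that Section 4d sets out to protect.

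The figures rest on SD 1.7. That is the SD of a day-to-day change in a single rating rather than of a between-arm difference of changes; it is used because it is the plan's own input. The split probabilities assume 12:12 enrolment and completion unrelated to dominance.

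**What to change.** - **Sections 3a and 4d:** state that the half-and-half split applies to completers, and give each replacement the same blocked-arm type as the person replaced, from a prepared allocation list.
- **Section 10a:** regress the between-arm change difference on an effect-coded term for blocked arm (dominant +1, non-dominant -1) and test the intercept, for the primary and secondary outcomes. At minimum, prespecify this as a sensitivity analysis. Say also how the nonparametric fallback would handle the factor.
- **Précis and Section 9:** reconcile the secondary outcome wording, so that it is clear whether each arm's baseline is subtracted.

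The cost is a few sentences and the list. Adjustment uses one degree of freedom (10 instead of 11), about 0.4 points of power if dominance has no effect (95.6% against 96.0%). With 6:6 kept, 12 completers still meet the 95% target, so the required number of completers does not change. If one arm type drops out more often, the cap of 24 could be reached before both halves are full. The adjusted analysis then still gives a valid test, with the lower power shown above.

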### **Details of Sensory testing paradigm**

Ratings of intensity and pleasantness of pressure and brushing: At baseline and after loss of sensation associated with A fibers, perception of deep pressure and gentle brushing will be tested on both arms. Deep pressure will be administered to the hand and wrist for approximately 20 seconds using a hand massager that applies oscillating pressure. Gentle brushing will be administered to the hand/forearm by a trained experimenter at a rate of approximately 3cm/second for approximately 15 seconds. Participants will rate intensity and pleasantness of each sensation on VAS scales with anchors of “no sensation” to “highest possible intensity” and from “extremely unpleasant” to “neutral” (midpoint) to “extremely pleasant.” Nearly identical VAS scales have been successfully used in our lab in numerous previous studies to distinguish the intensity versus pleasantness of sensory stimuli (e.g. [16, 17]). If cool perception is lost after light touch (not concurrently), A-delta fibers may be isolated and ratings can be collected again. Loss of cool and light touch often coincide, however [14]. Ratings of bad mood and anxiety will also be collected. They will be rated verbally on 0-10 scales (0 = none; 10 = worst you have experienced).

After placement of the tourniquet but before elimination of A-beta associated sensation, sensory testing will be conducted to monitor the block progression. Sensory testing will be conducted nearly continuously, which each test conducted approximately every ~1-2 minutes. All testing will be conducted distal to the block. The tests conducted during sensory monitoring may include the following:

Vibration perception (A-beta): A custom vibration device administering ~200 Hz vibration to the skin of the palm will be set for a random duration between 1-6 seconds. Participants will press a button (or similar response) when they perceive the onset and offset of the vibration.

Warm (C-fiber) and cool (A-delta) perception: Heat stimuli will be administered by the trained experimenter to the ventral surface of the forearm or palm using a contact

thermode (Medoc Pathway System; Medoc Ltd., Advanced Medical System, Israel). The Medoc thermode is used in accord with its FDA approved indication of human pain reception and transmission of sensory pathways. Warm threshold will start at approximately 32 °C and increase until the participant responds with a button press, eventually stopping at 50 °C. Cool threshold will similarly start at approximately 32 °C and decrease until the participants indicates perception of the cool, or to 0 °C. These threshold procedures are standard thermal testing procedures and have been used in our lab and elsewhere, including in currently approved NIH protocols [18].

Pinprick perception (A-delta): A pinprick (superficial; does not break skin) will be administered each test cycle and reaction time will be collected by a button press (or similar response).

Proprioception (A-alpha and A-beta): The experimenter and/or participant will move one finger up or down and the participant will indicate which direction the finger was moved in.

Pressure (unknown sensory afferent type): A quick pulse of pressure will be administered via a pressure algometric device. The participants indicate if they detected a pressure change and/or rate the intensity of the sensation from 0-10.

NRS ratings of current ongoing pain and discomfort (0-10) will be collected. 0 = no pain/no discomfort and 10 = intolerable pain or discomfort.

